### **E. Sample Size Reassessment**

No sample size reassessment is planned.

### **F. Interim Analyses or Timing of Analyses**

No interim analyses planned.

### **G. Test Sizes**

All confidence intervals will be two-sided with 95% coverage.

### **H. Multiple Comparisons**

No applicable for this study.

### **I. Analysis Sets**

Three analysis sets will be defined for use with various analyses.

#### **Full Analysis Set (FAS)**

The Full Analysis Set (FAS) will include all randomized patients who have at least 1 normalized Hb AUC measurement. Patients will be analyzed according to the treatment (MIR RBCs, REF RBCs) to which they were to receive in each period as assigned at randomization.

#### **Safety Set (SS)**

The Safety Set (SS) will include all randomized patients who undergo at least 1 episode of treatment after randomization. Patients will be analyzed according to the actual treatment received (MIR RBCs, REF RBCs) within each period. If a patient receives MIR RBCs at any time during a given period, patients will be summarized in the SS as receiving MIR RBCs for

that period. If a patient randomized to receive RBCs derived from Mirasol-treated WB only receives untreated RBCs within a given period, the patient will be summarized in the SS as receiving RBCs from untreated WB for that period. The safety analysis set will be used in reporting the safety issues in the study.

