10.3 Off-Protocol Transfusions

Off-protocol transfusions are defined as any RBC transfusions other than those to which the subject was randomized (MIR RBCs or REF RBCs), regardless of the indication or reason for the transfusion. Following the off-protocol transfusion, the subject will continue to receive transfusions according to the allocated treatment arm and will continue study participation.

For each off-protocol transfusion, if possible, all of the same data as for protocol specified transfusions will be captured in the eCRF, including the indication and reason for the off-protocol transfusion and any modifications to the RBC product.

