14.3 With Each RBC Transfusion Episode

The following procedures will be completed before, during, and after each study transfusion unless otherwise noted. These procedures will be completed for all transfusions occurring during the 50 -day wash-in period plus the subsequent 2 transfusion episodes (for endpoint assessment) during each of the 2 crossover treatment periods. The date and time of transfusion, number of units, and type of product transfused will be documented in the eCRF. For off-protocol RBCs transfusion, the following characteristics will also be collected: transfused volume, type of RBC unit (per ISBT code), and hematocrit (if known).

Visits on 1 Day Post Transfusion and 7 Days Post Transfusion may be conducted in the clinic or may utilize a remote nursing visit.

At Baseline the Investigator will identify and document the target post-transfusion (15 min) Hb level; with each transfusion episode, the Investigator will perform the following:

1. Calculate the volume of RBCs required to achieve the target Hb (identified at baseline)
 - a. $[(\text{desired hemoglobin}) - (\text{current hemoglobin})] \times (\text{body weight [kg]}) \times (3/\text{Hct of RBC units}) = \text{mL to transfuse}^{39}$

Note: 3 is constant in the formula above
2. If the post-transfusion (15 min) Hb is under 15% of the target Hb, then an additional transfusion should be considered. If the post-transfusion Hb is over 15% of the target Hb, this will be documented^{39,40}

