21.1.2 Safety Set

The Safety Set (SS) will include all randomized patients who undergo at least 1 episode of treatment after randomization. Patients will be analyzed according to the actual treatment received (MIR RBCs, REF RBCs) within each period. If a patient randomized to receive RBCs derived from Mirasol-treated WB only receives untreated RBCs within a given period, the patient will be summarized in the SS as receiving RBCs from untreated WB for that period. The safety analysis set will be used in reporting the safety issues in the study.

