### **A. Adverse Events**

All subjects will be assessed regularly for potential occurrence of adverse events (AE) from the treatment period until the subject is off study. The Medical Dictionary for Regulatory Activities (MedDRA; Version 16.1) will be used to code all adverse events to a System Organ Class (SOC) and Preferred Term (PT). The incidence of treatment-emergent AEs (TEAE) will be summarized and tabulated by treatment group. A TEAE is defined as any AE that occurs on or after the date of first transfusion.

The National Cancer Institute Common Terminology Criteria for Adverse Events (version 4.03; CTCAE) will be used to grade severity of all AEs. The severity of each AE will be assessed as mild, moderate, severe, life-threatening or fatal. Several occurrences of the same AE in one subject will be counted once and the one with worst severity will be counted.

The relationship of each AE to the study treatment or to study procedure will be grouped as related or unrelated. Any AE with a CRF description of definitely related, probably related, or possibly related will be considered related. Any AE

with a CRF description of not related will be considered unrelated. Several occurrences of the same AE in one subject will be counted once and the one with the closest relationship to study treatment or to study procedure will be counted. If an AE is missing the relationship to study medication, the event will be assumed to be related for analysis and summarization.

The number and percentage of patients reporting each PT will be summarized by the treatment received in the period of onset. Incidence of AEs by maximum reported CTCAE grade will also be tabulated within each arm. The SAEs and AEs leading to study discontinuation will be displayed. The following summaries will be presented:

- Overall summary of TEAEs
- TEAEs by SOC and PT. The number and percentage of subjects with at least one TEAE, as classified by system organ class (SOC) and preferred term (PT), will be summarized by treatment received in the period of onset. For these summaries, subjects with multiple events will be counted only once per SOC and preferred term.
- Study Treatment-related TEAEs by SOC and PT
- Study Procedure-related TEAEs by SOC and PT
- TEAEs by maximum CTCAE grade, SOC and PT
- Serious TEAEs by SOC and PT
- UADEs by SOC and PT
- Adverse transfusion reactions
- TEAEs causing discontinuation from the study
- All-cause mortality

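### The any-MIR period rule in the SAP Safety Set reports acute reactions to conventional units as MIR reactions in periods where a subject received both products

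*SAP*

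**What the plan says.** The protocol's Safety Set (section 21.1.2) states that "Patients will be analyzed according to the actual treatment received (MIR RBCs, REF RBCs) within each period". It covers a subject allocated to MIR who receives only untreated RBCs in a period, but has no rule for a period containing both products.

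The SAP (VI.I, Safety Set) fills that gap: "If a patient receives MIR RBCs at any time during a given period, patients will be summarized in the SS as receiving MIR RBCs". It keeps the other case: a subject randomized to MIR who "only receives untreated RBCs within a given period, the patient will be summarized in the SS as receiving RBCs from untreated WB".

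SAP IX.A sets the tabulation: "The number and percentage of patients reporting each PT will be summarized by the treatment received in the period of onset". The list of outputs that follows includes "Adverse transfusion reactions", with no attribution rule of its own.

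Mixed periods can arise. Protocol 10.3 defines an off-protocol transfusion as any RBC transfusion other than the allocated product, and says: "Following the off-protocol transfusion, the subject will continue to receive transfusions according to the allocated treatment arm". The product is known for each transfusion. Protocol 14.3 states: "The date and time of transfusion, number of units, and type of product transfused will be documented in the eCRF".

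**The concern.** Transfusion-related adverse events are a listed safety endpoint in both documents. Several reactions in protocol Table 19-1 belong in time to one transfusion: febrile reactions during or just after it, hypotension during it or within 1 hour, acute lung injury within 6 hours, dyspnea within 24 hours. For these, the relevant exposure is the product being given, not the label of a period that lasts more than 50 days.

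The efficacy analysis guards against this kind of mixing: SAP VIII.A removes off-protocol episodes from the primary endpoint. The reaction table has no counterpart. At stake is whether the reported MIR reaction frequency describes MIR units. If MIR units do cause more acute reactions, mixing in conventional units makes the excess look smaller, which is the less safe direction for a safety table.

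**Working it through.** The documents state no figure that depends on this rule, so there is none to reproduce. The check reads the rules case by case and then illustrates the size.

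**Step 1. Labels under the SAP rule**

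| Allocated period | Products received | SAP label | Acute reactions misattributed |
|---|---|---|---|
| MIR | MIR only | MIR | none |
| MIR | MIR and conventional | MIR | those after conventional units |
| MIR | conventional only | untreated | none |
| REF | conventional only | REF | none |
| REF | conventional and at least one MIR unit | MIR | those after conventional units; the subject has no REF data from that period |

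**Step 2. Episodes per period.** Inputs: 2-4 week transfusion intervals (protocol 11.2), and a 50-day wash-in followed by 2 episodes (protocol 10.1). Count transfusions on days 0, L, 2L and so on before day 50, then add 2.

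- L = 14: days 0, 14, 28, 42, so 4 + 2 = 6
- L = 21: days 0, 21, 42, so 3 + 2 = 5
- L = 28: days 0, 28, so 2 + 2 = 4

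One conventional episode in a MIR period is 1/6 to 1/4 (17-25%) of that period. One MIR episode in a REF period carries 5/6, 4/5 or 3/4 (83%, 80%, 75%) of the period's episodes into MIR although they were conventional.

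**Step 3. Conventional units substituted in MIR periods.** Let q be the share of MIR-period episodes that are conventional (not given; assumed 5%, 10%, 20%) and RR the true per-episode risk ratio, MIR to REF.

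- Apparent RR = (1 - q) × RR + q
- Share of MIR-labelled reactions that followed conventional units = q / [(1 - q) × RR + q]

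| True RR | Apparent RR at q = 5%, 10%, 20% | Share from conventional units |
|---|---|---|
| 0.5 | 0.525, 0.55, 0.60 | 9.5%, 18.2%, 33.3% |
| 1.0 | 1.00, 1.00, 1.00 | 5%, 10%, 20% |
| 2.0 | 1.95, 1.90, 1.80 | 2.6%, 5.3%, 11.1% |

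These ratios are per episode, whereas the SAP table counts patients. On the patient scale, assume 5 independent episodes and per-episode risks of 4% (MIR) and 2% (REF):

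- No mixing: (1 - 0.96^5) / (1 - 0.98^5) = 0.1846 / 0.0961 = 1.92
- q = 10%: MIR-period risk is 0.9 × 0.04 + 0.1 × 0.02 = 0.038, and (1 - 0.962^5) / 0.0961 = 0.1761 / 0.0961 = 1.83

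**Step 4. REF periods relabelled as MIR.** Let f be the proportion of subjects whose REF period contains a MIR unit (assumed), with equal per-episode risk p for both products and m = 5 independent episodes. MIR patient incidence = (1 - f) × [1 - (1 - p)^5] + f × [1 - (1 - p)^10]. REF incidence = 1 - (1 - p)^5.

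| p | REF incidence | MIR incidence at f = 2%, 5%, 10% | Ratio |
|---|---|---|---|
| 1% | 4.90% | 4.99%, 5.13%, 5.37% | 1.02, 1.05, 1.10 |
| 5% | 22.62% | 22.97%, 23.50%, 24.37% | 1.015, 1.04, 1.08 |

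Here an apparent excess appears although the products are equally safe, because the relabelled subjects contribute two periods to MIR.

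**The case against.** The strongest reply is that any-exposure classification is an accepted safety convention. Table 19-1 also lists delayed hemolytic reaction (2-14 days), post-transfusion purpura (7-10 days), graft-versus-host disease, infection and alloimmunization. For these, attribution to the last unit would be wrong and the period rule is sensible. This stands, and it limits the point to acute reactions. Nor is there a conflict with the protocol, which is silent on mixed periods.

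Second, relatedness to treatment and procedure is assessed and tabulated, study and other transfusions are listed, and off-protocol patterns are reported (SAP VII.C, VIII.C, IX.A). This helps a reader of individual cases, but none of it moves an event to the product that preceded it.

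Three stronger readings are tempting, and the documents do not support them.

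- A reader might infer that the reaction table is wrong whenever off-protocol transfusions occur. The cases in Step 1 show otherwise: a MIR period with only untreated RBCs is labelled correctly, and a mixed period matters only if a reaction follows a conventional unit.
- A reader might infer a bias against Mirasol. That is true of the event count but not of the comparison in general. Substitution pulls the contrast towards no difference and leaves it unchanged at equal risk; only relabelled REF periods, or conventional transfusions given in addition, push MIR incidence up.
- A reader might infer that conventional transfusions in MIR periods are expected. Protocol 10.3 only defines them, and SAP VIII.A says conduct will aim to eliminate or minimize them.

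**Conclusion.** The point holds for acute transfusion reactions in periods with both products. The Safety Set rule and tabulation by period of onset together report a reaction to a conventional unit as MIR, and no planned output corrects this.

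The size is unknown, because the documents give no off-protocol frequency. Under the assumed shares of 5% to 20%, a true per-episode ratio of 2.0 appears as 1.95 to 1.80. Under the assumed 2% to 10% of relabelled REF periods, equal risks appear as a patient-level ratio of about 1.02 to 1.10. The patient-level figures assume independent episodes with constant risk. If mixed periods are rare, the effect is small.

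The comparison is descriptive, with no test or margin, so no formal conclusion of the trial depends on it. It is a worthwhile, inexpensive improvement to a named safety endpoint.

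**What to change.** Keep the any-MIR period rule for delayed or cumulative outcomes and for the general AE tables. Add to the transfusion-reaction output in SAP IX.A a summary of acute reactions as follows:

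- Define acute as onset on the day of a transfusion or the day after. The documents do not state that AE onset time is collected, so the rule should work on dates. With transfusions typically 2-4 weeks apart, dates are sufficient in most cases.
- Attribute each acute reaction to the product actually transfused in that episode.
- Use transfusion episodes by product as the denominator, with episodes that contained both products as a separate row.
- Estimate the frequency by product with the GEE already specified in SAP VIII.C for off-protocol transfusions (logistic link, exchangeable correlation). Show counts and percentages alone if events are too few for the model.
- List events with partial onset dates separately. SAP VI.B may impute a missing day to the 15th or to the first dosing day, which cannot support attribution to an episode.

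The cost is SAP wording and one more programmed table. Product type and transfusion dates and times are already recorded, including for off-protocol units where possible. The downside is a small mixed-episode row to interpret. No change to trial conduct is involved.

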### **Per Protocol Set (PPS)**

The Per Protocol Set (PPS) will consist of all randomized patients who complete all episodes of treatment without any off-protocol transfusions, and who do not have any major CIP deviations. Patients in the PPS will be analyzed according to the treatment received. The study team will identify major CIP deviations prior to data analysis. The PPS will be used in the exploratory analysis of the primary efficacy endpoint.

## **J. Subgroups of Analysis Populations**

Data from subgroups of subjects in the defined analysis populations will be analyzed as specified below. These analyses will comprise descriptive summaries; the goal will be to identify signals of additional effects that analyses of data from the defined populations do not take into account. Such analyses will be considered exploratory. They may not be sufficient for drawing conclusions; hence, these analyses will not involve hypothesis testing.

## **K. Data Display Characteristics**

Data displays produced for this study will include three types: summary tables, data listings, and figures.

Data listings will simply list the data recorded on the case report form (CRF) or derived for each subject. They will be ordered by treatment, site, subject number, and time of assessment. Additional levels of ordering may be employed as appropriate. Data listings will not display subject initials.

Summary tables of post-baseline measures will be presented by treatment:

- MIR RBCs: RBCs will be derived from WB collected in CPD solution, treated with the Mirasol System for WB, LR, and stored in AS-3 for  $\leq$  21 days at 1 - 6°C
- REF RBCs: LR apheresis RBCs or WB-derived RBCs will be per site standard inventory

Patients will be randomized by treatment sequence:

- MIR RBCs followed by REF RBCs (MR) or
- REF RBCs followed by MIR RBCs (RM)

Summary tables of baseline measures will be presented by treatment sequence.

Continuous data will be summarized with the number of non-missing values, mean, standard deviation, minimum, median, and maximum. Categorical data will be summarized with the number of non-missing values and the numbers of values equal to each of the possible values. Percentages of patients with each of the possible values will be calculated from the number of patients in the relevant cohort of the corresponding analysis population, unless stated otherwise. Some continuous variables may also be grouped into categorical levels and evaluated in frequency tables.

All statistical analyses will be performed using SAS® software, Version 9.3, or higher.

## **VII. Subject Accountability**

### **A. Subject Disposition**

Enrollment and extent of participation in the study will be summarized by sequence (MR or RM) for all randomized patients. The number and percent of patients randomized, the number and percent of patients in each analysis set, and the number of patients who discontinued study early, and reason, will be presented.

Patient disposition data will be provided in a listing. A separate listing describing each patient's inclusion or exclusion status for each of the analysis sets will also be provided.

### **B. Protocol Deviations**

Protocol deviations will be captured by the site and reviewed by medical monitor. A listing of protocol deviations will be included.

### **C. Subject Characteristics**

#### ***Demographic and Baseline Characteristics***

Demographic and baseline information will be summarized for the FAS (only if significantly different than SS) and SS by treatment sequence:

- Age will be calculated at using the formula:  
Age = (Date of informed consent - Date of birth + 1) / 365.25 and truncated to complete years
- Sex (Male, Female)
- Ethnicity (Hispanic or Latino, Not Hispanic or Latino, Not Reported)
- Race (White, Black or African American, Native Hawaiian or Other Pacific Islander, Asian, American Indian or Alaskan Native, Other, Not Reported)

- Height (cm)
- Weight (kg)
- Prior RBC phenotyping or genotyping performed (Yes, No)
- Phenotyping/Genotyping results

Conversion factors and calculations for height, and weight:

- Height (in cm) = height (in inches) \* 2.54
- Weight (in kg) = weight (in lbs) \* 0.4536

### ***Medical and Surgical History***

Medical and Surgical History will be summarized by treatment sequence for the FAS and SS as the number and percentages of subjects with histories significant for each of the medical history/surgical history categories on the Medical History form.

All medical history will be provided as a listing for all subjects in SS.

### ***Thalassemia History and Transfusion History***

Primary diagnosis for Thalassemia and transfusion history (number of transfusion episodes in the last year; mean transfusion interval for the past 6 months; transfusion reactions in previous 6 months, and type of reaction) be summarized by treatment sequence for the FAS.

A subject listing will be presented for the SS.

### ***Study Treatment and Concomitant Medications***

All concomitant medications taken from the day of the first study transfusion and throughout the end of study treatment follow-up visit will be captured in the CRF. All study related RBC transfusions will be also recorded. Additionally, all blood products including off-protocol RBC transfusions, platelets, or plasma transfused until the end of study treatment follow-up visit will be recorded. The number of episodes of treatment received will be summarized by treatment (MIR RBCs, REF RBCs). The reason for treatment discontinuation will be associated with the last treatment arm prior to the time of discontinuation. Reasons for treatment discontinuation will be presented by treatment.

All concomitant medications will be coded to the therapeutic class and preferred term according to Mar 2016, Format C of World Health Organization (WHO) Drug Dictionary. Three listings will be provided:

- 1) All concomitant medications.
- 2) A listing of study related RBC transfusions
- 3) All other blood transfusions

## **VIII. Efficacy Analyses**

All efficacy analyses will be performed using the FAS unless otherwise noted. For the primary analysis, no imputation will be used for missing data. Sensitivity analyses will be performed on the primary endpoint using multiple imputation to impute missing values of the primary endpoint.

### **A. Efficacy Outcomes**

#### **Primary Endpoint**

The primary endpoint is normalized Hb AUC as a measure of the percent surviving RBCs. The normalized Hb AUC is calculated using the trapezoidal method on normalized Hb. The normalization is accomplished by dividing all post-transfusion Hb values by the 15-minute post-transfusion Hb level. The ratio is expressed as a percentage. A natural log-transform of the observed normalized Hb AUC will be utilized.

The normalized Hb AUC is expected to be calculated using four timepoints: the 15-minute post transfusion, 24-hour, Day 7, and end of transfusion interval (ie, pre-transfusion measure for the subsequent interval). If either the 24-hour or Day 7 measure is missing, the AUC will still be calculated using the following rule. If both are missing, or if either the 15-minute post transfusion or the end of transfusion interval are missing, then no AUC will be calculated for that interval.

A single value imputation approach will be used to estimate the missing percent decrease at either the 24 hour or Day 7 (but not both). The median of the observed normalized Hb levels (ie, percent decreases) for the treatment received at that particular time point and transfusion interval number will be used so that the AUC is based on 4 values of normalized Hb. This approach takes advantage of all the observed data rather than assuming an entire AUC is missing in the presence of a single missing Hb value.

The approximations are conservative in the sense that they bias towards inferiority in the case of missing Hb values for the normalized Hb AUC calculation.

The Hb will be collected within 1 hour before transfusion, 15 (+ 5) minutes, 24 ( $\pm$  6) hours, and 7 ( $\pm$  1) days after transfusion and at the end of study treatment follow-up. The transformed normalized Hb AUC values from the first 2 transfusion episodes after the 50-day wash-in for each period will be used to obtain a single measure associated with each treatment. If only a single

normalized Hb AUC value is available after the wash-in for an individual period, that single value will be used for analysis.

If a patient randomized to receive RBCs derived from Mirasol-treated WB in a particular period receives 2 successive off-protocol transfusion episodes (i.e., untreated RBCs) after completing the 50-day wash-in period, the primary endpoint for that period will be excluded from the analysis. If only 1 of the 2 successive transfusion episodes after the 50-day wash-in period is per protocol, only the primary endpoint associated with the per protocol transfusion episode will be analyzed. If at least 1 off-protocol transfusion occurs during a transfusion episode, the transfusion episode will be considered off-protocol. No off-protocol transfusions will be used for the primary analysis to minimize bias towards non-inferiority. The study will be executed to eliminate or minimize the risk of off-protocol transfusions.

